6.3. Measurements to Minimize Bias (including randomization + blinding)

The trial is an open-label, non-randomized, multicentre, prospective, first in human trial. Please see Statistical Section 11.

6.4. Trial Treatment, Product Packaging, Labelling

All treated subjects will receive a PRIMA System manufactured by Pixium Vision. The device consists of an implantable Retinal Implant, as well as a non-implanted Visual Processor.

The Retinal Implant is packaged in a sterile container together with a delivery system and labelled with the following information:

PRIMA Retinal Implant

Pixium Vision SA, [name], France

Exclusively for clinical investigations

Product reference

Serial number

Sterile/EO

Sterility expiration date

Single-use device.

The Visual Processor is labelled with the following:

PRIMA Visual Processor

Pixium Vision SA, [name], France

Exclusively for clinical investigations Serial number

Product reference

The serial numbers for each component will be documented in the respective CRFs.

6.5. Subject Participation

The subject is enrolled from the moment the subject signs and dates the patient informed consent form. The site will inform the sponsor about the enrolment of a patient immediately after he or she signed the informed consent. The sponsor keeps a log of enrolled patients and informs the sites as soon as the maximum number of subject is reached.

Document	Created by	Date	Page
CIP PRIMA FS-M Rev3	Clinical Affairs	19 June 2019	21 of 49

All subjects consented to participate in the trial are expected to complete the study throughout 36 months of follow-up. After the trial treatment of 36 month has been finished participants are asked to visit the hospital at minimum every 2 years as long as the implant is in the eye. For subjects that have finished the study the participating sites are asked to examine the subjects per standard of care and to report all device or procedure related adverse events to Pixium Vision.

Appendix A describes the schedule of procedure and follow up assessments.

6.6. Trial Stopping Rules and Discontinuation Criteria

The Sponsor or Principal Investigator may terminate the study at any point if:

- Permission for the study is revoked by a regulatory institution;
- A serious or unanticipated adverse event occurs which presents unacceptable risk for patients.¹

An individual may terminate their participation in the study at any point. It is recommended that the subject should discuss withdrawal from the study with their physician to ensure that withdrawal is managed in such a way as not to increase patient risk.

The trial will be interrupted if after implantation and activation of the first three subjects none of the subjects had visual perception evoked by the investigational device. In this case data will be reviewed and changes in the procedures and/or medical device may be required. If at least one of the first three subjects has perception elicited by the implant the study continues as planned with up to five subjects.

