6.2. Type and Design of Trial, Procedures and Stages

The study is an open-label, prospective, non-randomized, multi-centre, first in human study occurring at several investigational sites.

In this study, up to five subjects can be enrolled. In a first phase, three subjects will be enrolled and implanted. The study will be interrupted if none of the implanted subjects had visual perception elicited by the implant and/or an unacceptable device or procedure related adverse event occurred.

After an initial evaluative and training period, in which subjects will learn to use the device within a controlled laboratory environment, subjects will be allowed to take the device home and utilize it in their own environments for performance of specific tasks linked to the study objectives.

Procedures include:

1. Patient recruitment and Screening
2. Informed consent
3. Pre-Surgical ophthalmological examination
4. Baseline Vision testing
5. Implantation
6. Follow-up Assessments post-implantation
7. Silicone oil removal (if silicon oil was used)
8. Follow-up Assessments, stimulation assessments and home use

See Appendix A for a detailed schedule of procedures.

Document	Created by	Date	Page
CIP PRIMA FS-M Rev3	Clinical Affairs	19 June 2019	20 of 49

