6.8. Identification for Direct CRF Data Considered as Source Data

All investigators will be required to maintain study worksheets for ophthalmological and functional assessments, as well as clinical dictations, which may serve as source

¹ Pixium Vision continuously update the risk analysis for PRIMA. The risk analysis is performed according ISO EN 14971:2012. The data for severity and likelihood of individual adverse events are fed into the risk analysis. If this leads to one or more unacceptable risks, and no measure can be introduced to reduce the risks the complete study then, in compliance with ISO EN 14971:2012, the study will be stopped.

Document	Created by	Date	Page
CIP PRIMA FS-M Rev3	Clinical Affairs	19 June 2019	22 of 49

documentation. No information should be transferred to a CRF that does not have a corresponding source at the clinical site. See Appendix D.

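### Sections 6.2 and 6.6 and footnote 1 state inconsistent safety rules for the decision after the first three implants

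*Protocol*

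**What the plan says.** **Section 6.2.** The trial is staged: "In a first phase, three subjects will be enrolled and implanted". The rule for that stage follows: "The study will be interrupted if none of the implanted subjects had visual perception elicited by the implant", and the same sentence goes on "and/or an unacceptable device or procedure related adverse event occurred". Either trigger suffices, and the verb is mandatory.

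**Section 6.6, closing paragraph.** The same decision is stated again: "The trial will be interrupted if after implantation and activation of the first three subjects none of the subjects had visual perception evoked by" the device. A data review and possible changes to procedures or device are described for that case. The paragraph ends: "If at least one of the first three subjects has perception elicited by the implant the study continues as planned with up to five subjects". Neither the trigger nor the continuation sentence mentions safety.

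**Section 6.6, opening clause.** "The Sponsor or Principal Investigator may terminate the study at any point if" one of two listed conditions is met. The second is a serious or unanticipated adverse event that carries unacceptable risk for patients.

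**Footnote 1 to that condition** (printed at the foot of the page, under 6.8). Event data feed the sponsor's risk analysis. "If this leads to one or more unacceptable risks, and no measure can be introduced to reduce the risks", the study is to be stopped.

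**Context.** Sections 6.2 and 11.3 cap the trial at five subjects. The synopsis time schedule plans the last enrolment for June 2018. The page footers date this revision 19 June 2019.

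**The concern.** The decision after three implants is the only staged gate in a first-in-human surgical trial. It is stated twice, and the section headed as the stopping rules omits the safety trigger that the design section makes mandatory. The remaining safety text in 6.6 does not restore that trigger: it uses another class of event, another action and another degree of obligation. No sentence says which passage prevails, and nothing makes the continuation sentence subject to any of the safety provisions.

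What is at stake is whether the sponsor, an investigator or an ethics committee can read from the protocol what has to happen when the device works in someone but has also caused unacceptable harm. A secondary cost falls on the report, where the basis for going beyond subject three has to be traceable to a rule.

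**Working it through.** The protocol states no operating characteristic for the three-subject rule, so there is no figure to reproduce. The check is a comparison of texts.

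**Step 1: the provisions side by side**

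| Provision | Qualifying event | Action | Force |
|---|---|---|---|
| 6.2, first phase | No perception, and/or an unacceptable event related to device or procedure | Interrupt | Will |
| 6.6, three-subject paragraph | No perception in the first three | Interrupt and review | Will |
| 6.6, continuation sentence | At least one of three perceives | Continue to up to five | Unconditional as written |
| 6.6, opening clause | Serious or unanticipated event with unacceptable risk | Terminate | May |
| Footnote 1 | Unacceptable risk that no measure can reduce | Stop | Will |

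**Step 2: the four possible outcomes after three implants**

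| Perception | Unacceptable related event | 6.2 | 6.6 three-subject paragraph |
|---|---|---|---|
| 0 of 3 | No | Interrupt | Interrupt |
| 0 of 3 | Yes | Interrupt | Interrupt |
| At least 1 of 3 | No | Continue | Continue |
| At least 1 of 3 | Yes | **Interrupt** | **Continue** |

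The two sections part in the last row only.

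**Step 3: does the rest of 6.6 close the gap in that row?** Not fully.

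- *Force.* The opening clause permits termination; 6.2 requires interruption.
- *Event.* A related event that is judged unacceptable but is neither serious nor unanticipated meets 6.2 and falls outside the opening clause.
- *Threshold.* An unacceptable risk that can be reduced meets 6.2 but does not reach the stop in footnote 1.
- *Action.* Interrupting, terminating and stopping are different acts. A review step is described only for the no-perception interruption.

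**Step 4: size.** Places that depend on the decision: 5 − 3 = 2, at most. How often the divergent row would arise cannot be derived from the protocol, because it gives no rate of unacceptable related events. As an illustration only, let q be an assumed per-subject risk, independent between subjects. The chance of at least one such event in three is 1 − (1 − q)³:

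- q = 5%: 1 − 0.95³ = 14.3%
- q = 10%: 1 − 0.90³ = 27.1%
- q = 20%: 1 − 0.80³ = 48.8%

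These are upper bounds on the divergent row, which also needs at least one subject with perception.

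**The case against.** The best defence is that the provisions can be read as a ladder: a mandatory pause under 6.2, discretionary termination under 6.6, and a mandatory stop under the footnote if the risk cannot be reduced. On that reading, continuing as planned includes the safety interruption in 6.2, and the closing paragraph of 6.6 settles futility only. This is a sensible reading and may be what was intended. However, the text does not say it: there is no cross-reference and no order of precedence, and the qualifying events do not match.

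Other parts of the defence stand, and they rule out stronger readings that a reader might infer:

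- *That 6.6 forces continuation despite harm.* It does not. Its opening clause applies at any point, and the footnote compels a stop for irreducible risk. Only the continuation sentence, taken alone, lacks a safety condition.
- *That two sites could act in opposite ways.* The sponsor keeps the enrolment log (6.5), no implant is stored at a site (6.7), and a sponsor employee brings the implants to each operation (8.1.5). A site cannot proceed alone.
- *That the chance of at least one perceiver in three measures the defect.* Both sections use that criterion, so it says nothing about where they differ.
- *That an amendment would change the exposure of subjects 4 and 5.* On the planned dates, enrolment closed about a year before this revision. These are planned dates and do not prove what happened, but they make that consequence doubtful.
- *That the final report could not say what governed the decision.* It can, if the basis is recorded.

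**Conclusion.** The inconsistency is real and narrow. In one of four outcomes, with perception in at least one of three subjects and an unacceptable related event, 6.2 requires interruption. The closing paragraph of 6.6 says to continue, and the other safety text in 6.6 neither repeats the requirement of 6.2 nor takes precedence over the continuation sentence. At most two of five implants depend on it. No sample size, error rate or analysis is affected.

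The conclusion rests on the wording alone and needs no assumed rate. It is worth correcting because it concerns patient safety at the trial's only staged decision and costs little. It falls short of a critical defect, because 6.6 does give the power to end the study for unacceptable risk and because the decision may already have been taken. Which of the rules is clinically right is outside this review.

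**What to change.** Reconcile 6.2, 6.6 and footnote 1. State the rule once, and refer to it or repeat it in identical words elsewhere. The wording should settle four things:

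1. which events qualify (related to device or procedure, serious, unanticipated, or a stated combination);
2. which action follows (interrupt, terminate or stop), and how these relate to one another;
3. whether the action is required or permitted;
4. whether continuing beyond subject three depends on safety as well as perception.

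The sponsor and the clinicians choose the rule.

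Because planned last enrolment precedes this revision, the final report should also state which rule was applied, and on what data, before subjects 4 and 5 were implanted, if they were.

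The cost is amendment wording and a short statement in the report. No data collection or analysis changes.

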6.7. Accountability Procedures

A log of all implants and patients will be maintained. No implant will be stored at the clinical sites. Any explanted devices will be immediately returned to the sponsor.

6.8. Identification for Direct CRF Data Considered as Source Data

All investigators will be required to maintain study worksheets for ophthalmological and functional assessments, as well as clinical dictations, which may serve as source

¹ Pixium Vision continuously update the risk analysis for PRIMA. The risk analysis is performed according ISO EN 14971:2012. The data for severity and likelihood of individual adverse events are fed into the risk analysis. If this leads to one or more unacceptable risks, and no measure can be introduced to reduce the risks the complete study then, in compliance with ISO EN 14971:2012, the study will be stopped.

Document	Created by	Date	Page
CIP PRIMA FS-M Rev3	Clinical Affairs	19 June 2019	22 of 49

documentation. No information should be transferred to a CRF that does not have a corresponding source at the clinical site. See Appendix D.

6.9. Participating clinical sites

The trial is designed as a multi-centre trial and the sponsor keeps a list of all participating clinical sites. Since the study uses competitive patient recruitment it is possible that all patients are enrolled in one site.

7. Selection and Withdrawal of Patients

Patients will be assessed for inclusion in the study based on the criteria outlined below. If patients meet the inclusion criteria, they will be invited to participate in the study. After signing the Informed Consent, a detailed study ophthalmological exam will occur in order to verify all Inclusion/Exclusion criteria. If any patients fail to meet Inclusion/Exclusion criteria after the complete study pre-surgical ophthalmological exam, he/she will be withdrawn from the study and considered a screening failure. Once patients meet all Inclusion/Exclusion criteria they will be implanted with the device.

7.1. Patient Inclusion Criteria

Patients will be included in the study provided that he or she:

- Is 60 years or older at the date of enrolment;
- Has a confirmed diagnosis of advanced dry age related macular degeneration with an atrophy size of at least 3 optic disc diameters;
- Has best corrected visual acuity of the study eye of logMAR 1.3 (20/400) or worse measured by ETDRS;
- Has no foveal perception measured by micro-perimetry in the study eye (≤ 4 dB on Opko scale or equivalent)²;
- Has a study eye that is able to perceive light;
- Has useful vision on the non-study eye;
- Has a refraction of study eye between -3 and $+4$ (limits included) for patient with IOL (there is no refraction criteria for patients with natural lens);
- Understands and accepts the obligation to present for all schedule follow-up visits.
- Patient signed informed consent

² Please see protocol appendix G for a detailed microperimetry protocol

Document	Created by	Date	Page
CIP PRIMA FS-M Rev3	Clinical Affairs	19 June 2019	23 of 49

7.2. Patient Exclusion Criteria

Patients will be excluded from the study if he or she:

- Has cataracts that may influence the visual function of the study eye;
- Has an aphakic study eye
- Had cataract surgery in the last 1 month;
- Active sub-macular choroidal neovascularization in the study eye;
- Has any disease (other than study allowed diseases) or condition that affects retinal function of the study eye (e.g., central retinal artery/vein occlusion, end-stage diabetic retinopathy, retinal detachment, infectious or inflammatory retinal disease, severe glaucoma, optic neuropathy, myopic chorio-retinal atrophy etc.);
- Has an implanted telescope in one eye;
- Has any disease or condition that prevents adequate examination of the study eye including, but not limited to, corneal degeneration that cannot be resolved prior to implantation. Note, that this criterion is also important for the function of the implant;
- Has an endothelia cell count of less than 1000 cells/mm² in the study eye;
- Suffers from nystagmus;
- Has any disease or condition that precludes the understanding or communication of the informed consent, study requirements or test protocols (e.g., deafness, severe multiple sclerosis, amyotrophic lateral sclerosis, severe neuritis, etc.);
- Has a history of epileptic seizure;
- Has a history of chronic or recurrent infection or inflammation that would preclude participation in the study;
- Has a known sensitivity to the contact materials of the implant (iridium oxide, silicon-carbide and titanium);
- Presents with hypotony in the study eye;
- Presents with hypertony in the study eye;
- Has another active implanted device (e.g. cochlear implant, pacemaker) that may interfere with the device function, or diagnoses requiring such an active implant;
- Has active cancer or a history of intraocular, optic nerve or brain cancer and metastasis;
- Is an immune-suppressed subject (e.g., due to HIV positive diagnosis, etc.);
- Is carrier of multi-resistant germs;
- Is receiving anticoagulation therapy that cannot be adapted to allow eye surgery;
- Is participating in another investigational drug or device study that may interfere with the present study;
- Patients with recurrent or chronic inflammations or infections are excluded from the study. Specifically, patients with the following disorders are excluded:

Document	Created by	Date	Page
CIP PRIMA FS-M Rev3	Clinical Affairs	19 June 2019	24 of 49

- Common inflammation – severe chronic and consuming diseases that frequently associated with infection (e.g. Crohn disease, Whipple's disease);
- Active inflammation in the area of the eye (e.g. herpes of cornea and/or conjunctiva, recurrent blepharoconjunctivitis, horedolum, chalazion);
- Has a severe psychological disorder. When in any doubt, an expert assessment needs to be arranged to clarify whether the patient's psychological health is suitable for the trial. In any doubts of the subjects psychological status a clinical psychologist, psychologist or the community doctor/general practitioner should be involved. The patient must have the legal capacity to sign the informed consent;
- Has severe renal, cardiac, hepatic etc. organ diseases;
- Has head dimension that are incompatible with the Visual Interface.
- Has too high and unrealistic expectation (e.g., believes that a benefit is guaranteed or expect normal vision after surgery);

7.3. Criteria and Procedure Specifications for Subject Withdrawal

Patients may withdraw their consent for participation in the investigation at any time.

Patients may also be withdrawn from the study if:

- He or she significantly fails to comply with the study follow-up schedule;
- In the opinion of the treating investigator continuation in the study jeopardizes the subject's health and/or well-being;
- There are significant protocol violations surrounding the patient's original inclusion in the study;
- Either the Sponsor or a governing regulatory authority discontinues the study.

[figure not shown]
8. Treatment Plan and Follow-Up Periods

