6.1. Specific Statements of Primary and Secondary Endpoints

The primary efficacy endpoint is the assessment of the device performance to demonstrate principal functionality of the PRIMA system. It is assessed by measuring the capability of the patient to perceive light at specific locations. To prove the functionality of the device, patients are tested with the device on and off. At 6 weeks, 3, 6, 12, 18, 24, and 36 months after implantation. In this feasibility study the fundamental function of the PRIMA device will be tested by OCTOPUS visual field measurement.

The visual acuity will be measured with the Landolt test as a secondary endpoint for all subjects once it is approved. The first time this new test is measured depends on the follow-up time point the subject is approaching and will be the earliest after 18 months follow-up. Afterwards the Landolt C test will be measured at 24 and 36m.

The primary safety endpoint of the study will involve an analysis of the incidence, severity and duration of all adverse events at 1 day, 1 week, 1, 1.5, 3, 6, 12, 18, 24, and 36 months. The safety of the implanted device will be assessed in a series of regular ophthalmologic examinations designed to capture any pathological changes in the eye as a result of device implantation.

All adverse events according to section 10 will be recorded. Every adverse event will be identified by a name defined by the investigator (e.g. retinal detachment). During later analyses of the safety the “incidence” of every adverse event will be compared to adverse event rates of other comparable devices which are already on the market for similar indications (e.g. ARGUS II, Second Sight Medical Products, USA). The investigator rates the “severity” of an adverse event by rating it as mild, moderate or severe. He/she also check if the criteria for serious adverse events according to Section 10 are fulfilled. The investigator also rates the likelihood of adverse events being device related or procedure related by choosing the appropriate term defined in Section 10. All adverse events are followed until they are solved or medically stable. Medically stable events are events that are not expected to be completely resolved but reached a status where no further treatment or treatment change will be necessary. The “duration” of an adverse event is defined as the time between date of onset and the date when the event is resolved or medically stable status has been reached.

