8.1. Treatment Plan

Patients will be followed for 36 months post implantation. As part of follow-up, all subjects will be required to undergo ophthalmologic examination, testing, and/or training. Appendix A contains the master schedule of events occurring at each follow up visit. Several sessions may be required per follow-up period to complete all scheduled tasks. Appendices C contains sub protocols with specific instructions for each of the assessments. A summary of procedures and assessments is found over-page followed by a listing of study follow up intervals. In addition to the follow up visits listed in Appendix A, training and tuning sessions will take place.

Document	Created by	Date	Page
CIP PRIMA FS-M Rev3	Clinical Affairs	19 June 2019	25 of 49

The investigational plan is structured as follows:

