8.1.12 Explantation

Explantation of the device will only take place to resolve significant adverse events or in case of early device failure. In case of a planned explantation the risk and benefit of the procedure should be carefully evaluated in light of the individual conditions of the patient eye.

Document	Created by	Date	Page
CIP PRIMA FS-M Rev3	Clinical Affairs	19 June 2019	33 of 49

If the implant failed to work within the 36 months study follow up because of a deterioration of the implant that leads to a nonfunctional device, it will be explanted, except the individual condition of the subject's eye does not allow a safe explantation. The explanted device will be brought back to Pixium Vision for a detailed analysis of the implant failure.

In the absence of significant adverse events or device failures, the device remains implanted after study subject participation ends. The physician will follow up with the patient per hospital standard of care, and no study data will be collected after the subject exited the study.

If an explantation will be necessary because of medical issues or an early device failure, the procedure will be done in the same manner as the implantation but instead of introducing the implant in the sub retinal space the implant will be removed.

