8.3. Subject follow-up after study exit

All subjects consented to participate in the trial are expected to complete the study throughout 36 months of follow-up. After the trial treatment of 36 months has been finished participants are asked to visit the hospital at minimum every 2 years as long as the implant is in the eye. For subjects that have finished the study the participating sites are asked to examine the subjects per standard of care and to report all device or procedure related adverse events to Pixium Vison.

9. Assessment of Performance

This section describes the procedure to measure the performance endpoints of the device.

The performance endpoints of this study are defined in terms of elicitation of visual perception. In this feasibility study the performance of the device will be measured using OCTOPUS visual field measurement. The function of the device is demonstrated by measuring the subject's capability to carry out tasks with the device "on" compared to the

Document	Created by	Date	Page
CIP PRIMA FS-M Rev3	Clinical Affairs	19 June 2019	34 of 49

device switched off (wearing the visual interface). In addition, the visual field is measured at baseline and without the device at each follow-up interval according Appendix A. In addition to Octopus, the visual acuity will be measured according to Appendix C3.

The performance endpoint is measured at a number of time points throughout the study. All endpoint testing will be conducted under the supervision of qualified Health Care Professionals.

Appendix A contains a listing of stimulation sessions at various time points throughout the study. Appendix C contains the end point testing procedures.

10. Assessment of Safety

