10.2. Procedures for Reporting and Recording Adverse Events

Subjects will be carefully monitored during the study for possible Adverse Events (AEs) from the time the subject signs the Patient Informed Consent form to the completion of their participation in the study. Any AE observed will be fully investigated by the Investigator and classified in line with the definitions of the ISO14155:2011, which are shown below.

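### Section 7.3 lets an implanted subject be withdrawn from the whole study for health reasons or missed visits without keeping safety data collection open, so new and late events before month 36 can go unrecorded

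*Protocol*

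**What the plan says.** Section 7.3 opens its list of investigator- and sponsor-side reasons with "Patients may also be withdrawn from the study if". Two of the reasons matter here: "He or she significantly fails to comply with the study follow-up schedule" and "In the opinion of the treating investigator continuation in the study jeopardizes the subject's health and/or well-being". The other two are a serious violation around the subject's inclusion and discontinuation of the study by the sponsor or an authority. The text makes no distinction between subjects before and after implantation, or between stopping device use or testing and leaving follow-up.

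The safety plan is set elsewhere:

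- Section 8.1: "Patients will be followed for 36 months post implantation".
- Section 6.1: "The primary safety endpoint of the study will involve an analysis of the incidence, severity and duration of all adverse events", at time points up to 36 months. It also says that events are followed until they are resolved or stable. Section 10.2.10.2 says much the same, ending at resolution, a chronic state or loss to follow-up.
- Section 10.2: adverse events are monitored "from the time the subject signs the Patient Informed Consent form to the completion of their participation in the study".
- Section 8.1.12: the physician continues with standard hospital care and "no study data will be collected after the subject exited the study".
- Section 8.3 (and Section 6.5 in the same terms), on the period after the 36 months: "For subjects that have finished the study the participating sites are asked to examine the subjects per standard of care", with a request to report device- or procedure-related events.
- Section 11.4.3: missing data are not replaced.

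**The concern.** The exposure is an implant that normally stays in the eye. The safety question therefore continues after a subject stops using the glasses or attending tests. If leaving the study also closes the safety record, an event that begins after exit is not counted, even though it falls within the 36 months that the primary safety endpoint covers.

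Under the health criterion, exit is triggered by the subject's condition, so the missing time is related to the outcome being measured. The likely direction is too few late events. Section 6.1 plans to compare event incidence with that of marketed devices, so an undercount would flatter the investigational device. An analysis plan cannot recover examinations that were never made, which is why this has to be settled in the protocol.

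**Working it through.** **Figures in the plan.** The maximum of five implanted subjects (Section 11.3) is given without a calculation, so there is no stated result to reproduce. The main check is to read the rules against each other. The arithmetic only gives scale.

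**Step 1: follow one case through the text.** Suppose an implanted subject is withdrawn at month 12 on the health criterion, with the implant in place.

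- The event that led to withdrawal is recorded. Under Sections 6.1 and 10.2.10.2 it should be followed to an outcome. Sections 10.2 and 8.1.12 point the other way once participation has ended, so even this needs reconciling.
- An event that starts at month 20 is outside the monitoring window in Section 10.2, because participation ended at month 12.
- Section 8.1.12 says that no study data are collected after exit. Its paragraph opens with subjects free of significant adverse events and device failure, but the statement on data is not limited to those who completed 36 months.
- Sections 6.5 and 8.3 speak of subjects who have finished the study, after 36 months. A subject withdrawn at month 12 is not clearly among them. Even if included, only related events are requested, whereas the endpoint is all adverse events.
- Section 6.6 recommends a talk with the physician, but only where the subject chooses to leave, and it requires no data.

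No visible section keeps the scheduled safety examinations, or reporting of new events, going to month 36 for this subject.

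**Step 2: subject-months.** Planned: 5 × 36 = 180. For one subject withdrawn at month t, the loss is (36 − t)/180. The times are assumptions.

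| Month of exit | Lost | Share of 180 |
|---|---|---|
| 12 | 24 | 13.3% |
| 18 | 18 | 10.0% |
| 24 | 12 | 6.7% |

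In each case four of five subjects (80%) have 36-month data. Exit at month 6 would cost 30/180 = 16.7%. However, the synopsis plans the last visit for August 2021, which puts the last implantation near August 2018. This revision is dated 19 June 2019, about ten months later, so on schedule that case had already passed.

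**Step 3: what one lost late event does.** Suppose only one subject would have had a given late event, and that subject is the one withdrawn. With full follow-up the result is 1/5, exact 95% interval 0.5% to 71.6%. As recorded it is 0/4 among those followed to month 36; the upper limit is 1 − 0.025^(1/4) = 60.2%. If the full cohort is kept as denominator it is 0/5, with upper limit 1 − 0.025^(1/5) = 52.2%. Either way an observed event becomes none.

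**Step 4: loss unrelated to harm, for comparison.** The chance of seeing at least one event is 1 − (1 − p)^n. For assumed late risks p of 10%, 20% and 30% it is 41.0%, 67.2% and 83.2% with n = 5, and 34.4%, 59.0% and 76.0% with n = 4. Withdrawal for health is not unrelated to harm, so these figures do not capture the bias.

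**The case against.** The case on the other side has real weight, and most of it limits the point.

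- A reader might infer that Section 7.3 takes harmed subjects out of follow-up. It does not require that. Withdrawal is permitted, and Sections 6.5 and 8.3 expect every consented subject to complete 36 months. Early loss is possible, not certain.
- A reader might infer that the complication behind a health withdrawal disappears from the record. It does not. It is recorded, goes to the clinical event committee if serious or related, and under Sections 6.1 and 10.2.10.2 is followed to an outcome. What is exposed is new or later events and the scheduled examinations.
- A reader might infer that the lost time always belongs to the harmed subject. That follows from the health criterion. For missed visits it is plausible, but nothing in the protocol shows it.
- A reader might infer that a withdrawn subject drops out of the safety analysis. Section 11.1 defines the safety cohort by eligibility and implantation, so an eligible implanted subject stays in for events up to exit. Only the later denominators shrink.
- Some withdrawn subjects may no longer carry the implant, since Section 8.1.12 provides for explantation.
- With at most five subjects, described individually and with missing-data patterns reported (Section 11.4.1), an early exit would be visible to the reader.
- The consent form and Appendices A, D and F are not available here and could contain an exit provision.

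None of this supplies a rule that keeps new events and examinations coming in to month 36. A visible gap is better than a hidden one, but the data are still missing.

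**Conclusion.** The point holds in a limited form. As written, the protocol allows an implanted subject to leave the whole study for non-compliance or health reasons, and its rules on what happens next can leave new and late events unrecorded within the 36-month primary safety endpoint. Under the health criterion the bias would be towards too few late events; for missed visits the direction is not established.

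The size is modest in time and larger in information: 7% to 13% of planned subject-months for one withdrawal between months 12 and 24, and one fifth of the 36-month observations. This assumes five implanted subjects, one withdrawal at an assumed time, and no exit provision in the appendices or consent form. The protocol should be changed, but the text does not show that any subject will be lost or that recorded events will be dropped.

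**What to change.** Add a paragraph to Section 7.3:

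- After implantation, withdrawal for non-compliance, for health or for an inclusion violation ends performance testing and sessions but not safety data collection.
- Unless the subject withdraws consent to follow-up, adverse event reporting continues to month 36, together with those scheduled safety examinations that the investigator considers appropriate.
- The reason for withdrawal and the status of each adverse event at exit are recorded.
- Missed visits are recorded as missed.
- Discontinuation of the study by the sponsor or a regulator is outside this rule.

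Then reconcile Sections 8.1.12, 8.3 (with 6.5) and 10.2 with Sections 6.1 and 10.2.10.2, so that they agree on which data are collected after exit and for whom. Check that the consent form matches.

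The cost is one paragraph and a few aligned sentences. The visits are already in the schedule and no new procedure is needed. The small downside is that sites keep contacting subjects who attend poorly.
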